6.1 Screening Procedures

Unless otherwise stated, the baseline measurement for any given variable will be defined as the last value obtained prior to the first dose of study drug.

Informed Consent

Signed informed consent will be obtained from the subject or the subject's legally acceptable representative before any study-specific procedures are undertaken or before any prohibited medications are withheld from the subject in order to participate in this study. Informed consent is also required for pharmacodynamic sample collections.

Medical and Oncologic History

The following will be collected during the Screening Visit:

- Complete medical history, including documentation of any clinically significant medical conditions.
- Detailed oncologic history, including:
 - Date of CLL diagnosis
 - Cytogenetics (if known from prior testing)
 - o IgVH mutation status (if known from prior testing)
 - Somatic mutations in CLL cells (if known from prior testing)

- Treatments administered (including approximate dates, response to treatment if known, and reason for treatment discontinuation).
- Detailed and concomitant medication usage including dates of usage and dosing information for all medications and supplements taken.
- Prior to the first treatment visit (C0D1), any changes observed from the Screening assessments (prior to dosing) will be recorded in the subject's medical history.

Physical examination

Physical examination performed should include evaluate of presence and degree of enlarged lymph nodes in two dimensions in cervical, supraclavicular, axillary, and inguinal regions; hepatomegaly; and splenomegaly. Additional physical exam of other organ systems are per clinical standard of care.

If during physical examination, signs or symptoms suggestive of Richter's Syndrome are observed further assessment (i.e, node biopsy or PET scan) should be considered if clinically indicated to assess for or confirm Richters.

Vitals signs

Body temperature, weight, blood pressure, and pulse will be measured.

ECOG performance status

Subject's performance status will be assessed based on the ECOG system. See Appendix A for description/definition.

Clinical Laboratory Tests:

Local laboratories will be utilized to process and provide results for the clinical laboratory tests. Investigator should review, initial, and date the laboratory results. The following labs are collected during the screening period:

- CBC with differential (automated or manual)
- Comprehensive Metabolic Panel
- Hepatitis B and C serologies. This a standard of care assessment prior to administration of any anti-CD20 therapy and not done for the sole purpose of research). HBsAg, anti-HBs, total anti-HBc, IgM anti-HBc, HCV ab or RNA. If during screening a subject present with a positive Hepatitis B core antibody, Hepatitis B Viral DNA PCR test should be performed to rule out an active infection. If there are known results of hepatitis serologies within 6 months without at risk exposure, they do not need to be repeated.
- If female of child-bearing potential: serum pregnancy test within 14 days of initiation of therapy on trial.

Computed Tomography (CT) Scans (or Magnetic Resonance Imaging [MRI])

A CT scan must be performed within 30 days prior to study drug administration for all subjects. A CT scans should include chest, abdomen, and pelvis sequences. Contrast is preferred though can be omitted if contraindication. A contrast-enhanced MRI of chest, abdomen, and pelvis may be used for subjects in whom a CT is medically contraindicated (example: contrast allergy). Whichever method is used at Screening is preferred to be used consistently through the duration of the study for that subject.

Justification: The CT or MRI scans at baseline is a standard of care assessment prior to initiation of venetoclax in order assess tumor burden and risk for TLS, as this will guide optimal management to mitigate the risk of TLS. This test is necessary to determine if some patients may safely start venetoclax with outpatient monitoring, infusion center monitoring, or inpatient monitoring. Although this is also part of the primary endpoint assessment, it is also a needed and standard test for patient safety and in accordance with the prescribing information when venetoclax is prescribed even outside of clinical trials.

Initiation and prescription of prophylactic medication

After confirmation of eligibility, patients are prescribed allopurinol 300 mg PO daily (or dose adjusted per clinical indication such as renal failure, or alternate medication per clinician judgement), and instructed to start 3 days prior to treatment initiation.

6.2 Cycle 0: HDMP + Rituximab

Cycle 0 is 28 days in duration.

On Day 1, the following are done:

- Medical history, physical exam, and vital signs
- Laboratory examinations: CBC w/ differential, comprehensive metabolic panel, phosphorous, uric acid, and LDH. (Potassium, Phosphorous, Calcium, uric acid, and creatinine are necessary and clinically indicated to assess for possible tumor lysis syndrome, and not simply as markers of disease burden).
- Collection of correlative pharmacodynamic sample, prior to treatment (4, approximately 8-10 mL anticoagulated tubes – ACD or heparin)
- Methylprednisolone 1000 mg/m2 IV
- Rituximab 100 mg IV

On Day 2 and 3, the following are done:

- Vital signs
- Laboratory examinations: CBC w/ differential, comprehensive metabolic panel, phosphorous, uric acid, and LDH. (Potassium, Phosphorous, Calcium, uric acid, and

creatinine are necessary and clinically indicated to assess for possible tumor lysis syndrome, and not simply as markers of disease burden).

- Methylprednisolone 1000 mg/m2 IV
- Rituximab 375 mg/m2 IV

On Day 4, the following are done:

- Vital signs
- Laboratory examinations: CBC w/differential, comprehensive metabolic panel, phosphorous, uric acid, LDH
- Rituximab 375 mg/m2 IV

Between Day 15 and Day 28 of Cycle 0, disease burden is reassessed to determine risk of TLS prior to Venetoclax initiation, including:

- Laboratory examinations: CBC w/ differential, comprehensive metabolic panel, phosphorous, uric acid, LDH
- CT or MRI of thorax, abdomen, and pelvis. IF medically necessary to reassess TLS risk.
 Areas that did not have enlarged lymph nodes 1.5 cm or greater in long-axis diameter may
 be skipped for this radiographic reassessment. (Justification: This is again a necessary
 procedure to determine Tumor Burden and to optimally manage and mitigate TLS risk for
 patients prior to starting Venetoclax).

6.3 Cycle 1: Venetoclax Ramp-up

Cycle 1 is 35 days in duration and consists of venetoclax dose-ramp up, following standard dosing and TLS risk mitigation strategies as per Venetoclax prescribing information.

On Day 1 of Cycle 1, the following are completed:

- History and physical examination including vital signs.
- Current medications will be recorded in the subject's medical record.
- Laboratory examinations: CBC w/differential, comprehensive metabolic panel, phosphorous, uric acid, LDH Collection of correlative research sample
- Dispense and take initial dose of Venetoclax 20 mg PO.
- Tumor lysis syndrome monitoring as per Appendix D and E, which includes additional chemistry monitoring, potential IV fluid administration, and potential inpatient hospitalization if clinically indicated and in accordance with venetoclax standard of care.

On Day 2 of Cycle 1, the following are completed:

- Laboratory examinations: hematology (CBC w/differential), comprehensive metabolic panel, phosphorous, uric acid, LDH.
- Dispensing Venetoclax 20 mg 6 day supply
- 2nd dose of venetoclax 20 mg PO after labs are resulted and reviewed by treating physician or investigator.
- Patients continue venetoclax 20 mg PO daily C1D2 C1D7.

On Day 8 of Cycle 1, the following are completed:

- Current medications will be recorded in the subject's medical record.
- Laboratory examinations: CBC w/differential, comprehensive metabolic panel, phosphorous, uric acid, LDH
- Dispense and take initial dose of Venetoclax 50 mg PO dose level.
- Tumor lysis syndrome monitoring as per Appendix D and E, which includes additional chemistry monitoring, potential IV fluid administration, and potential inpatient hospitalization if clinically indicated and in accordance with venetoclax standard of care.

On Day 9 of Cycle 1, the following are completed:

- Laboratory examinations: CBC w/differential, comprehensive metabolic panel, phosphorous, uric acid, LDH
- Dispensing Venetoclax 50 mg 6 day supply
- 2nd dose of venetoclax 50 mg PO after labs are resulted and reviewed by treating physician or investigator.
- Patients continue venetoclax 50 mg PO daily C1D9 C1D14.

On Day 15 of Cycle 1, the following are completed:

- Current medications will be recorded in the subject's medical record.
- Laboratory examinations: CBC w/differential, comprehensive metabolic panel, phosphorous, uric acid, LDH
- Dispense and take initial dose of Venetoclax 100 mg PO dose level. (7 day supply).
- Tumor lysis syndrome monitoring as per Appendix D and E, which includes additional chemistry monitoring, potential IV fluid administration, and potential inpatient hospitalization if clinically indicated and in accordance with venetoclax standard of care.

(Only required if High Tumor Burden prior to venetoclax initiation): On Day 16 of Cycle 1, the following are completed:

- Laboratory examinations: CBC w/differential, comprehensive metabolic panel, phosphorous, uric acid, LDH
- 2nd dose of venetoclax 100 mg PO after labs are resulted and reviewed by treating physician or investigator.
- Patients continue venetoclax 100 mg PO daily C1D16 C1D21.

On Day 22 of Cycle 1, the following are completed:

- Current medications will be recorded in the subject's medical record.
- Laboratory examinations: CBC w/differential, comprehensive metabolic panel, phosphorous, uric acid, LDH
- Dispensing and initial dose of Venetoclax 200 mg PO dose level. (7 day supply).
- Tumor lysis syndrome monitoring as per Appendix D and E, which includes additional chemistry monitoring, potential IV fluid administration, and potential inpatient hospitalization if clinically indicated and in accordance with venetoclax standard of care.

(Only required is High Tumor Burden prior to venetoclax initiation): On Day 23 of Cycle 1, the following are completed:

- Laboratory examinations: CBC w/differential, comprehensive metabolic panel, phosphorous, uric acid, LDH
- 2nd dose of venetoclax 200 mg PO after labs are resulted and reviewed by treating physician or investigator.
- Patients continue venetoclax 200 mg PO daily C1D23 C1D28.

On Day 29 of Cycle 1, the following are completed:

- Current medications will be recorded in the subject's medical record.
- Laboratory examinations: CBC w/differential, comprehensive metabolic panel, phosphorous, uric acid, LDH
- Dispensing and initial dose of Venetoclax 400 mg PO dose level (7 day supply).
- Tumor lysis syndrome monitoring as per Appendix D and E, which includes additional chemistry monitoring, potential IV fluid administration, and potential inpatient hospitalization if clinically indicated and in accordance with venetoclax standard of care.

(Only required is High Tumor Burden prior to venetoclax initiation): On Day 30 of Cycle 1, the following are completed:

• Laboratory examinations: CBC w/differential, comprehensive metabolic panel,

phosphorous, uric acid, LDH

- 2nd dose of venetoclax 400 mg PO after labs are resulted and reviewed by treating physician or investigator.
- Patients continue venetoclax 400 mg PO daily C1D31 onward.

6.4 Cycles 2 to 6: Venetoclax + Rituximab

All subsequent cycles are 28 days each in duration.

On Day 1 of Cycle 2-6, the following are completed:

- History and physical examination including vital signs.
- Current medications will be recorded in the subject's medical record.
- Laboratory examinations: CBC w/differential, comprehensive metabolic panel, phosphorous, uric acid
- Dispensing of Venetoclax 400 mg PO dose (or highest tolerated dose), 30 day supply.
- Rituximab 500 mg/m2 IV

6.5 Cycles 7-24: Venetoclax

Cycles 7-24 are 28 days each in duration

Patients are scheduled to be seen in clinic every 3 months

On Day 1 of Cycles 7, 10, 13, 16, 19, and 22, the following are completed:

- History and physical examination including vital signs.
- Current medications will be recorded in the subject's medical record.
- Laboratory examinations: CBC w/differential, comprehensive metabolic panel, phosphorous, uric acid
- Dispensing of Venetoclax 400 mg PO dose (or highest tolerated dose), 90 day supply.

In addition, on Day 1 of Cycle 10

- CT or MRI of thorax, abdomen, and pelvis. Areas that did not have enlarged lymph nodes (greater than 1.5 cm in long-axis diameter on the prior scan) or spleen may be skipped for this radiographic reassessment.
- Marrow biopsy and aspirate if clinical examination is consistent with a complete remission (ie, absolute lymphocyte count less than 4k/uL) and if clinically indicated to determine subsequent therapy (eg: stopping therapy if undetectable minimal residual disease).

6.6 End of Study Assessment

Within 2 weeks before or after Cycle 24, Day 28, the following are completed:

- History and physical examination including vital signs.
- Current medications will be recorded in the subject's medical record.
- Laboratory examinations: CBC w/differential, comprehensive metabolic panel.
- Collection of correlative sample.
- CT or MRI of thorax, abdomen, and pelvis.
- Marrow biopsy and aspirate if clinical examination is consistent with a complete remission (ie, absolute lymphocyte count less than 4k/uL) and if clinically indicated to determine subsequent therapy (e.g.: stopping therapy if undetectable minimal residual disease).

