- Continue allopurinol, acyclovir, and septra (or equivalent drugs, unless contraindication). Must stop fluconazole 7 days prior to first venetoclax dose.
- Week 1: Venetoclax 20 mg daily
- Week 2: Venetoclax 50 mg daily
- Week 3: Venetoclax 100 mg daily
- Week 4: Venetoclax 200 mg daily
- Week 5: Venetoclax 400 mg daily
- TLS Monitoring per venetoclax package insert.

Cycles 2-6 (28 days in duration each): Venetoclax + Rituximab

- Continue Venetoclax 400 mg PO daily (or highest tolerated dose)
- Rituximab 500 mg/m2 on day 1 of each cycle.

Cycle 7-26: Single agent Venetoclax

- Continue Venetoclax 400 mg PO daily (or highest tolerated dose)

End of Study:

- Marrow biopsy and aspirate to assess for detectable CLL (MRD)

Long-term f/up: No specific visits required. With patient consent, date of progression or next CLL therapy will be recorded.

Concomitant Medications:

- It is prohibited to take other intended CLL therapies concurrently, including purine analog, alkylating drugs, other anti-CD20 monoclonal antibody, ibrutinib, Idelalisib, etc. Corticosteroids are permitted (in cycle 0 as CLL therapy; in cycles 2-6 as anti-CD20 infusion reaction prophylaxis; and at other times for treatment of conditions other than CLL).
- Required wash out for the above is 5 half-lives or 1 month, whichever is shorter.
- GCSF, EPO, and blood transfusion are not restricted, and can be used as clinically indicated or as per clinician judgement.
- TLS prophylaxis is recommended from 3 days prior to Cycle 0 Day 1 until Cycle 2 Day 1: Allopurinol 300 mg daily (dose modified if needed; alternative uric acid lowering medication can be substituted).
- Anti-Infection Prophylaxis is recommended from 3 days prior to Cycle 0 day 1:
- Fluconazole 100 mg daily (or alternative per clinician discretion) until Cycle 1 Day 21;
- Acyclovir 400 mg BID (or alternative per clinician discretion) until Cycle 3 Day 1 (or may continue longer)
- Septra DS BID 2 days/week (or alternative per clinician discretion) until Cycle 3 Day 1 (or may continue longer)

It is prohibited to receive live viral vaccines or other investigational agents.

Version: 5 (Dec-2024)

Subject Withdrawal or Treatment Discontinuation:

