4.0 Study Design

4.1 Description

This is a single center, open-label, pilot/feasibility study designed to evaluate the feasibility of HDMP/Rituximab as an approach to decrease TLS risk for patients who receive venetoclax for treatment of CLL/SLL.

Patients with CLL/SLL who require therapy, and have disease burden meeting criteria for Medium or High Tumor Burden (based on: lymph nodes >/= 5 cm in diameter and/or absolute lymphocyte count >/= 25k/uL) are enrolled.

- Patients will receive HDMP + Rituximab for 1 cycle, followed by reassessment of Tumor burden.
- Patients will then initiate venetoclax dose ramp-up, with ramp-up schedule according to venetoclax package insert.
- If Tumor Burden classification is still Medium/High after 1 cycle of HDMP + rituximab, patients are also given the option to repeat a 2nd cycle of HDMP + Rituximab prior to the venetoclax dose ramp-up.

Upon completion of ramp-up (venetoclax to 400 mg), all patients will continue Venetoclax 400 mg (or highest tolerated dose) for up to 2 years. Patients will also continue rituximab 500 mg/m2 q 28 days through Cycle 6.

4.2 Endpoint Assessment:

- 1. Assessment of the disease burden after a maximum of 2 cycles of HDMP + Rituximab is the primary endpoint for HDMP/R as an approach to decrease risk of TLS.
- 2. Assessment of the disease burden after 1 cycle of HDMP + Rituximab.
- 3. Assessment of the disease burden after 2 cycles of HDMP + Rituximab (for the subset of patients that do not meet criteria for low tumor burden after 1 cycle).
- 4. Clinical and laboratory TLS events between start of treatment and the completion of venetoclax dose-ramp up (Cycle 2, Day 1)
- 5. Presence or absence of detectable MRD in the marrow will be assessed after approximately 9 months of venetoclax and completion of treatment.
- 6. Radiology assessment after approximately 9 months of venetoclax and at the completion of therapy, and as clinically indicated (unless prior imaging studies are without measurable disease)

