8.2 International Working Group CLL (iwCLL) Clinical Response Assessment

Criteria for response will utilize the 2008 IWCLL Guidelines for response, which includes clinical, hematological, and bone marrow feature:

Complete response: Requires all of the following for a period of at least two months from completion of therapy:

- Absence of significant lymphadenopathy (e.g. >1.5cm in diameter) on physical exam;
- No hepatomegaly or splenomegaly on physical exam;
- Absence of constitutional symptoms;
- Blood counts within the following values: lymphocytes < 4,000/uL, polymorphonuclear leukocytes >1500/ μ L, platelets >100,000/ μ L, hemoglobin >11.0 g/dL (untransfused); absences of clonal lymphocytes;
- Bone marrow aspirate and biopsy must be normocellular for age with <30% of nucleated cells being lymphocytes. Lymphoid nodules must be absent. If the marrow is hypocellular, a repeat determination should be performed in one month.
- The marrow should be analyzed by flow cytometry and/or immunohistochemistry to demonstrate that the marrow is free of clonal B- CLL cells.
- A CT scan or MRI documenting absence of significant lymphadenopathy should be performed if previously abnormal.

• Patients who fulfill the criteria for CR after induction with the exception of a persistent cytopenia that is believed to be treatment related will be considered CR with incomplete bone marrow recovery (CRi). Additionally, patients who fulfill the criteria of CR with exception of having bone marrow lymphoid nodules will be considered a nodular PR.

Partial response: Requires at least 2 of the following criteria from group A, and at least one of the criteria from group B, and for a period of at least 2 months:

Group A:

- ≥50% decrease in peripheral absolute lymphocyte count from pretreatment value, or less than 4,000/uL
- ≥50% reduction in lymphadenopathy by examination or scan, or less than 1.5cm in size.
- ≥50% reduction in splenomegaly (cm below costal margin) by examination or scan
- ≥50% reduction hepatomegaly (total liver span) by examination or scan
- 50% reduction in marrow infiltrate or B-lymphoid nodules

Group B:

- Polymorphonuclear leukocytes ≥1,500/µL or 50% improvement from pre-treatment value:
- Platelets >100,000/µL or 50% improvement from pre-treatment value;
- Hemoglobin >11.0 g/dl (un-transfused) or 50% improvement from pre-treatment value.

Progressive Disease: Characterized by any one of the following events:

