8.3 Minimal Residual Disease Assessment

Primary clinical efficacy analysis will be assessment of marrow for detectable CLL after 24 cycles (or sooner if treatment is discontinued early) by flow cytometry and immunohistochemistry per standard practice by local hematopathologist. A threshold of 0.01% will define undetectable versus detectable minimal residual disease (MRD).

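### Sections 6.5 and 6.6 make the endpoint marrow conditional on remission and clinical indication, while 4.2 and 8.3 state it without condition, so the CR and MRD rates depend on who is biopsied

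*Combined protocol and SAP*

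**What the plan says.** Two parts of the protocol describe the same marrow differently.

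- **Conditional.** Section 6.6 lists "Marrow biopsy and aspirate if clinical examination is consistent with a complete remission (ie, absolute lymphocyte count less than 4k/uL", and adds that it must also be "if clinically indicated to determine subsequent therapy (e.g.: stopping therapy if undetectable minimal residual disease". The visit is fixed by "Within 2 weeks before or after Cycle 24, Day 28, the following are completed". Section 6.5 repeats both conditions for Cycle 10 Day 1, with the second worded "if clinically indicated to determine subsequent therapy (eg: stopping therapy if undetectable minimal residual disease".
- **Unconditional.** Section 4.2 item 5 says "Presence or absence of detectable MRD in the marrow will be assessed after approximately 9 months of venetoclax and completion of treatment". Section 8.3 describes its leading clinical efficacy analysis as "assessment of marrow for detectable CLL after 24 cycles (or sooner if treatment is discontinued early"; the sentence carries no remission or indication requirement. The synopsis, in its short procedures list under End of Study, has "Marrow biopsy and aspirate to assess for detectable CLL (MRD".

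Section 9.1 makes the CR rate and the undetectable-MRD rate secondary endpoints, each at about 9 months of venetoclax and at completion. Among the requirements for CR, section 8.2 includes "Bone marrow aspirate and biopsy must be normocellular for age with <30% of nucleated cells being lymphocytes".

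**The concern.** An endpoint measurement should be triggered by the visit schedule or by a fixed criterion, not by whether the result would change a patient's care. Under 6.5 and 6.6 the second condition is a judgement made patient by patient. Two investigators treating identical patients could produce different sets of marrows, and therefore different CR and MRD rates. Under 4.2 and 8.3 that could not happen. Site staff work from section 6 and the analysis is written from sections 4, 8 and 9, so the conflict would probably surface only when the rates are compiled and the missing marrows cannot be recovered.

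**Working it through.** **1. The plan's own figures.** The document gives no expected CR rate, MRD rate or number of marrows. Its only design figures concern debulking. With 10 patients in stage 1, stopping at 2 or fewer responses, and rejecting at 9 or more of 17:

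- Early stopping under the null: P(Bin(10, 0.30) ≤ 2) = 0.3828 (stated 38.3%).
- P(reject) = Σ over x = 3 to 10 of P(Bin(10, p) = x) × P(Bin(7, p) ≥ 9 − x). This is 0.0402 at p = 0.30 (stated 0.04) and 0.8008 at p = 0.60 (stated 80%).

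These reproduce and do not depend on any marrow.

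**2. The sections side by side.**

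| Place | Time point | Condition on the marrow |
|---|---|---|
| 4.2 item 5 | about 9 months and completion | none |
| 8.3 | after 24 cycles, or earlier if treatment stops early | none |
| Synopsis (brief list) | end of study | none |
| 6.5 | Cycle 10 Day 1 | remission on examination and clinical indication |
| 6.6 | C24D28 ± 2 weeks | remission on examination and clinical indication |
| 6.8 | after withdrawal from all therapy | no visit required except HBV follow-up |

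**3. Which endpoints are exposed.**

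- *CR.* The first condition is glossed as a lymphocyte count below 4k/uL. CR under 8.2 needs lymphocytes below 4,000/uL as well, so a patient who fails the first condition on that count could not be a CR anyway. The second condition is the one that removes possible CRs.
- *MRD.* Both conditions select. Anyone failing either has no result, and those tested are likely responders.
- *ORR.* PR needs two of five group A items, only one of which is marrow infiltrate, and one group B blood-count item. It can be met without a marrow.
- *Repair rules.* Section 9.7.1 counts unassessable patients as failures for the primary endpoint only. Section 9.9 rules out imputation. No denominator is given for CR or MRD.

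**4. Is a stopping decision still open at the end-of-study visit?** Cycle 1 lasts 35 days and later cycles 28.

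- End of Cycle 24: 35 + 23 × 28 = 679 days; 679 / 30.4375 = 22.3 months.
- End of Cycle 26: 35 + 25 × 28 = 735 days; 735 / 30.4375 = 24.1 months.

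If venetoclax ends at Cycle 24 (6.5), the example of stopping therapy has little left to decide. If it runs to Cycle 26 (synopsis), 735 − 679 = 56 days of treatment remain. At Cycle 10, day 35 + 8 × 28 = 259 (8.5 months), treatment is ongoing and the example fits.

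**5. Illustration, with assumed counts.** Seventeen treated, m marrows done, u undetectable. The bounds for all 17 run from u/17 to (u + 17 − m)/17. Intervals are exact 95%, as in 9.7.

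| Assumed m, u | Among biopsied | Over all 17 | Bounds for all 17 |
|---|---|---|---|
| 10, 8 | 80% (44–98%) | 47% (23–72%) | 47–88% |
| 6, 5 | 83% (36–99.6%) | 29% (10–56%) | 29–94% |

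For CR, assume 6 of 17 patients meet every other criterion and would have a clean marrow. Counting unbiopsied patients as non-CR, which is a further assumption, the rate is 6/17 = 35% (14–62%) if all six are biopsied, 2/17 = 12% (1.5–36%) if two are, and 0/17 if none is. Each omitted marrow costs 1/17 = 5.9 percentage points. Counting only patients with a marrow, the first two cases become 6/6 and 2/2, both 100%.

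**The case against.** The best defence is that the second condition is deliberate. A marrow biopsy is invasive, and restricting it to patients whose care may depend on it is a clinical choice the investigator is entitled to make. These are secondary endpoints in a 17-patient pilot. The synopsis list calls itself brief and refers to the main protocol, so its silence on conditions proves little. All of this stands. It leaves the conflict between 6.5/6.6 and 4.2/8.3 untouched: a deliberate restriction still has to appear where the endpoint is defined.

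A reader might infer that the second condition can hardly be met at C24D28, so that almost no end-of-study marrows would be done. The documents do not support that. Stopping therapy is given only as an example, which leaves other indications open. The synopsis continues venetoclax to Cycle 26, and section 4.1 allows up to 2 years.

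A reader might also cite the schedule of events (Table 3) as planning both marrows outright. It marks them with a note (e) whose wording is not in the text available for review and might contain the same conditions. It supports neither side.

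**Conclusion.** The sections disagree on who has the endpoint marrow, and nothing in section 9 resolves it. If 6.5 and 6.6 are followed, the CR and undetectable-MRD rates at both time points depend partly on whom the investigator chooses to biopsy. The conclusion rests on the wording of 4.2, 6.5, 6.6, 8.2 and 8.3 alone.

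The size cannot be derived from the documents; every percentage in step 5 rests on assumed counts. In particular, a reader might infer that a patient in clinical remission without a marrow is rated PR, so that the CR rate falls from 35% towards zero. Section 8.2 denies such a patient a CR, but no section says how the patient is then classed; not evaluable is equally possible. The falling CR rate holds only if unbiopsied patients stay in the denominator as non-CR, which the plan does not state.

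This should be corrected, but it does not threaten the trial's main conclusion on debulking.

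**What to change.** Reconcile 6.5 and 6.6 with 4.2, 8.3 and the synopsis so that one rule, applied the same way to every patient, states who has the endpoint marrow and when. The rule should cover patients who stop early, where 8.3 expects an earlier marrow and 6.8 requires no visit. Which clinical condition, if any, to keep is for the sponsor and investigator to decide.

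If the clinical-indication condition stays:

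- restate the CR and MRD endpoints in 8.3 and 9.1 as covering only patients with a marrow;
- report how many of all treated patients had a marrow at each time point, and why the others did not;
- give the rates over all treated patients as well, with unbiopsied patients shown as a separate category.

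The cost of this route is protocol wording, a recorded reason for each marrow not done, and a few extra lines in the results tables; the CR and MRD claims become narrower. If the sections are instead aligned on an unconditional marrow, some patients would have a biopsy that 6.6 does not now require. That is a real burden and should be weighed openly.
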